5.5 Prior and Concomitant Therapy

Subjects should not take any vitamin D and/or bone metabolism therapy other than the study drug. Excluded therapies include any non-study prescribed dose of 1 α -hydroxylated vitamin D analogs (calcitriol, paricalcitol and doxercalciferol), calcimimetics, bisphosphonates, denosumab, teriparatide, preotact, calcitonin and other drugs that may affect bone metabolism. Glucocorticoids and hormone replacement therapy should remain at the same dose throughout the study.

All concomitant medication usage from Visit 1 until completion of the study will be recorded.

Cytochrome P450 inhibitors, such as ketoconazole, atazanavir, clarithromycin, indinavir, itraconazole, nefazodone, nelfinavir, ritonavir, saquinavir, telithromycin or voriconazole, may inhibit enzymes involved in vitamin D metabolism (CYP24A1 and CYP27B1), and may alter serum levels of calcifediol.

Cholestyramine has been reported to reduce intestinal absorption of fat-soluble vitamins and may impair the absorption of calcifediol, the active ingredient in CTAP101 Capsules. Phenobarbital or other anticonvulsants or other compounds that stimulate microsomal hydroxylation reduce the half-life of calcifediol.

5.5.1 Phosphate Binder and Elemental Calcium Therapy

Use of phosphate binders is prohibited throughout the study. Elemental calcium may be prescribed during the screening visit to ensure the dietary intake is within the range of 1,000-1,500 mg per day. The overall dose of elemental calcium intake should remain stable throughout the study.

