Approximately 80 subjects will be randomized 1:1:1:1 (approximately 20 per arm) to receive one of the listed study medications with a sufficient quantity of a non-alcoholic beverage to enable swallowing of the capsules:

- 1) CTAP101 Capsules 60 mcg once daily outside of the phase 1 unit at bedtime, except on Days 1 and 29 when dosing will occur in the phase 1 unit in the morning before breakfast.
- 2) IR calcifediol 266 mcg in the phase 1 unit before breakfast on the mornings of Day 1 and Day 29.
- 3) Cholecalciferol 300,000 IU (high-dose) in the phase 1 unit before breakfast on the mornings of Day 1 and Day 29.
- 4) Paricalcitol 1 mcg plus cholecalciferol 800 IU (low-dose) once daily outside of the phase 1 unit in the morning before breakfast, except on the mornings of Days 1 and 29 when dosing will occur in the phase 1 unit before breakfast.

After 4 weeks of treatment, subjects who are receiving paricalcitol will double the dose to 2 mcg plus cholecalciferol 800 IU once daily in the morning before breakfast provided that (a) the plasma iPTH has not decreased by at least 30% from pretreatment BL and remains above 70 pg/mL, (b) corrected serum calcium is <9.8 mg/dL, and (c) serum phosphorus is <5.5 mg/dL. Subjects who are receiving CTAP101 Capsules, IR calcifediol or cholecalciferol (300,000 IU) will not undergo upward dose titration.

Subjects will reduce the dose of study medication per the schedule below in the event that plasma iPTH is confirmed to be <30 pg/mL, corrected serum calcium is confirmed to be >10.3 mg/dL, or serum phosphorus is confirmed to be >5.5 mg/dL. Subjects will suspend dosing if plasma iPTH is confirmed to be <15 pg/mL or corrected serum calcium is confirmed to be >11.0 mg/dL, and will resume dosing when plasma iPTH is ≥30 pg/mL and corrected serum calcium is <9.8 mg/dL per the dose schedule below.

Dose reduction (if needed):

CTAP101: decrease to 30 mcg per day (from 60 mcg per day)

IR calcifediol: hold Day 29 dose

Cholecalciferol 300,000 IU: hold Day 29 dose

Paricalcitol: decrease dose to 1 mcg per day (from 2 mcg per day)

Cholecalciferol 800 IU will not be adjusted

In the event that a dose reduction is required for a subject receiving the minimum dosage of CTAP101 Capsules (30 mcg per day) or paricalcitol (1 mcg per day), the subject will suspend dosing and resume when iPTH is ≥ 30 pg/mL and corrected serum calcium is <9.8 mg/dL at the same minimum dosage.

Dose resumption (if needed):

CTAP101: 30 mcg per day

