5.3 Dose Reduction Criteria

Subjects will reduce the dose of medication at any time by the schedule below in the event that plasma iPTH is confirmed to be <30 pg/mL, corrected serum calcium is confirmed to be >10.3 mg/dL, or serum phosphorus is confirmed to be >5.5 mg/dL. Subjects will suspend dosing if plasma iPTH is confirmed to be <15 pg/mL or corrected serum calcium is confirmed to be >11.0 mg/dL, and will resume when plasma iPTH is \geq 30 pg/mL and corrected serum calcium is <9.8 mg/dL per the dose schedule below.

Dose reduction:

CTAP101: decrease to 30 mcg per day (from 60 mcg per day)

IR calcifediol: hold Day 29 dose

Cholecalciferol 300,000 IU: hold Day 29 dose

Paricalcitol: decrease dose to 1 mcg per day (from 2 mcg per day).

Cholecalciferol 800 IU will not be adjusted during the study period

In the event that a dose reduction is required for a subject receiving the minimum dosage of CTAP101 Capsules (30 mcg per day) or paricalcitol (1 mcg per day), the subject will suspend dosing and resume when iPTH is \geq 30 pg/mL and corrected serum calcium is <9.8 mg/dL at the same minimum dosage.

Dose resumption:

CTAP101: 30 mcg per day

Paricalcitol: 1 mcg per day

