5.3.1 Overdose and Toxicity

Excessive administration of calcifediol, cholecalciferol, or paricalcitol can cause hypercalciuria, hypercalcemia, hyperphosphatemia, or over suppression of intact PTH. Common symptoms of vitamin D overdosage may include constipation, decreased appetite, dehydration, fatigue, irritability, muscle weakness, or vomiting.

Treatment of acute accidental overdosage with calcifediol, cholecalciferol, or paricalcitol should consist of general supportive measures. If the overdosage is discovered within a short time, induce emesis or perform gastric lavage to prevent further absorption. Obtain serial serum and

urine calcium measurements, and assess any electrocardiographic abnormalities due to hypercalcemia. Discontinue supplemental calcium. Treat with standard medical care if persistent and markedly elevated serum calcium levels occur.

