5.5.2 Diet Restrictions

There are no study specific dietary restrictions. Subjects should follow their dietary plan if one has been prescribed. Changes in prescribed dietary phosphorus or calcium therapy are discouraged and any changes during the study should be captured in the electronic case report form (eCRF).

Subjects will maintain a dietary intake during the study of approximately 1,000-1,500 mg per day of elemental calcium per dietary counseling and, as necessary, administration of a daily calcium supplement. Subjects will complete a dietary questionnaire on Visit 1 and receive counseling from a dietitian on their dietary calcium intakes, if needed.

Subjects will report to the phase 1 unit on the mornings of Day 1 and Day 29 after an overnight fast. They will receive standardized meals while housed in the phase 1 unit. These meals will contain 400 mg of elemental calcium and will be administered at approximately 2, 6, and 10 hours post-dose.

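### Protocol 5.3 answers confirmed hypercalcemia through study drug only, while 5.5.1 and 5.5.2 advise against changing calcium intake; the two bolus arms have no dose left to hold after Day 29

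*Protocol*

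**What the plan says.** Protocol 5.3 lowers the study dose when, among other triggers, "corrected serum calcium is confirmed to be >10.3 mg/dL", and suspends dosing above 11.0 mg/dL. For the two arms dosed only on Days 1 and 29, the listed actions are "IR calcifediol: hold Day 29 dose" and "Cholecalciferol 300,000 IU: hold Day 29 dose". Calcium supplements are not mentioned at either threshold. The Protocol Synopsis (Dosing Plan) carries the same rule ("Subjects will reduce the dose of study medication per the schedule below"), and SAP 3.3 restates it; neither adds anything about calcium.

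On calcium itself, Protocol 5.5.1 lets a supplement be prescribed at screening to bring intake to 1,000-1,500 mg/day, then says: "The overall dose of elemental calcium intake should remain stable throughout the study". Protocol 5.5.2 repeats the range and adds: "Changes in prescribed dietary phosphorus or calcium therapy are discouraged". It asks for any change to be recorded. Neither section refers to hypercalcemia or to 5.3.

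Protocol 5.3.1 does contain the instruction "Discontinue supplemental calcium". The paragraph it stands in opens: "Treatment of acute accidental overdosage with calcifediol, cholecalciferol, or paricalcitol should consist of general supportive measures".

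**The concern.** Hypercalcemia is the main expected toxicity of every arm. The plan has a threshold for acting on it, yet the action list omits the one other calcium input that the protocol controls. Followed as written, the calcium sections point the other way: leave intake alone.

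This matters most in the bolus arms after Day 29. There, neither the reduction rule nor the suspension rule has a dose to act on, and the drug already given cannot be taken back. What is at stake is the care of individual subjects. No estimate, error rate or sample size is affected.

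**Working it through.** The plan gives no figure on this point, so the check is a comparison of text, a count, and a test of whether the number affected can be estimated.

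**1. Action on study drug, by arm (Protocol 5.2 and 5.3)**

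| Arm | Confirmed above 10.3 mg/dL | Confirmed above 11.0 mg/dL | Dose left to act on after the Day 29 dose |
|---|---|---|---|
| CTAP101 | 60 to 30 mcg/day; suspend if already at 30 | suspend | yes, daily |
| Paricalcitol + 800 IU | 2 to 1 mcg/day; suspend if already at 1; 800 IU unchanged | suspend | yes, daily |
| IR calcifediol | hold Day 29 dose | suspend | none |
| Cholecalciferol 300,000 IU | hold Day 29 dose | suspend | none |

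No cell contains a calcium action.

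**2. Calcium text.** Section 5.5.1 advises stability for the whole study. Section 5.5.2 gives a range and discourages change. Section 5.3.1 stops the supplement, but as treatment of accidental overdosage. A subject who took exactly the assigned dose and has a confirmed value of 10.4 mg/dL meets the 5.3 trigger and is not an overdose case. No other section of the protocol body links the trigger to the supplement.

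**3. Extent of the period without a dose action**
- Subjects: 20 + 20 = 40 of about 80.
- Time: 57 - 29 = 28 days, of 57 - 1 = 56 treatment days.
- Scheduled visit days in that window: 30, 31, 36, 43, 50 and 57, which is six. Chemistry is drawn at each, so a high value would be seen.

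**4. Is drug still present in that window?** This assumes first-order decline at the half-lives in the annexed labels.
- IR calcifediol (Appendix 2, 18 to 21 days), 28 days after dosing: 0.5^(28/18) = 0.34 to 0.5^(28/21) = 0.40 remaining.
- 25(OH)D3 after cholecalciferol (Appendix 4, peak near day 7, half-life about 50 days): 0.5^(21/50) = 0.75 of the peak, or 0.5^(28/50) = 0.68 if counted from dosing.

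These figures show only that exposure continues to Day 57. They are not a risk of hypercalcemia, nor the benefit of stopping a supplement.

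**5. Number affected** = (subjects with a confirmed event) x (share of them taking a supplement).
- The second factor is given nowhere.
- For the first, in the high-dose cholecalciferol arm, the Appendix 3 label rate of 0.1% to 1% gives 20 x 0.001 = 0.02 to 20 x 0.01 = 0.2. That rate is at labelled doses, not 300,000 IU in stage 3-4 CKD.
- Two paricalcitol trials in Protocol 1.12 report 2% and nearly 23% with two consecutive values above 10.5 mg/dL: 20 x 0.02 = 0.4 to 20 x 0.23 = 4.6. Those trials ran longer than 8 weeks, used a higher threshold, and concern an arm that keeps a dose action throughout.

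No usable count follows.

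**The case against.** The strongest reply is that the conflict is soft and investigators are not left without means.

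- **The wording is advisory.** Section 5.5.1 says *should* and 5.5.2 says *discouraged*. Section 5.5.2 asks for changes to be recorded, and 6.7 gives calcium-supplement changes their own eCRF page. A reader might infer that the protocol forbids stopping a supplement. It does not.
- **Other routes exist.** Section 6.6.6 defines clinical significance partly by whether treatment is needed. Section 6.8 permits withdrawal for an important laboratory change, and withdrawal ends the stable-intake advice. The overdosage paragraph in 5.3.1 closes by sending persistent, marked calcium elevation to usual medical care.
- **Having nothing to hold after Day 29 is inherent in a two-dose regimen.** A reader might call that a design defect in itself. It is not; it only makes the silence about other measures matter more.

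All of this stands, and it limits the severity. It does not close the gap. None of these routes is tied to the 10.3 mg/dL trigger, and withdrawal is a blunt response where stopping a supplement might suffice. A site that follows the calcium advice literally would leave the supplement in place.

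Three further readings are not supported. The persistence percentages and the paricalcitol rates do not measure harm in the bolus arms. No bias between arms follows, because the calcium policy is the same in all four. The renal-impairment statements in the cholecalciferol labels concern who should receive the product, not how to respond to a high calcium value, and form no part of this point.

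**Conclusion.** The point holds as a minor subject-safety gap. At confirmed corrected calcium above 10.3 or 11.0 mg/dL the plan acts on study drug only. Its calcium sections advise against change without an exception, and its one stop instruction is attached to accidental overdosage. In two of four arms no dose action remains for 28 of 56 days.

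Confidence is high for the text and low for the consequence. The number of subjects affected is likely small, but it cannot be computed: the documents give neither the share on a supplement nor an applicable event rate for the bolus arms. The conclusion rests on sites following 5.5.1 and 5.5.2 as written; an investigator who uses clinical judgement can already do the sensible thing.

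**What to change.** Add to Protocol 5.3, for all arms: *At confirmed corrected serum calcium >10.3 mg/dL, stop any calcium supplement; it may be restarted once corrected serum calcium is <9.8 mg/dL.* The restart level is the calcium level at which 5.3 already lets suspended dosing resume.

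Add *except as required by 5.3* to the stable-intake sentence in 5.5.1 and to the intake and no-change sentences in 5.5.2. Carry both changes into the copies: the dose-reduction text in the Protocol Synopsis (Dosing Plan) and SAP 3.3, and the maintain-intake text in the Protocol Synopsis (Study Design), Protocol 3.1 and SAP 3.3.

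The drafting cost is a sentence, a clause and their copies. No new data collection is needed, because 6.7 already provides the eCRF page.

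There is a scientific cost. Calcium intake would change after an event, possibly to below 1,000 mg/day, so later calcium and iPTH changes in those subjects could not be credited to the drug action alone. If confirmation comes from a repeat sample before the next visit, the stop might also prevent a second consecutive visit above 10.3 mg/dL. Drug reduction already has that effect, and SAP 9.3 counts one-visit cases as well.

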5.5.2 Diet Restrictions

There are no study specific dietary restrictions. Subjects should follow their dietary plan if one has been prescribed. Changes in prescribed dietary phosphorus or calcium therapy are discouraged and any changes during the study should be captured in the electronic case report form (eCRF).

Subjects will maintain a dietary intake during the study of approximately 1,000-1,500 mg per day of elemental calcium per dietary counseling and, as necessary, administration of a daily calcium supplement. Subjects will complete a dietary questionnaire on Visit 1 and receive counseling from a dietitian on their dietary calcium intakes, if needed.

Subjects will report to the phase 1 unit on the mornings of Day 1 and Day 29 after an overnight fast. They will receive standardized meals while housed in the phase 1 unit. These meals will contain 400 mg of elemental calcium and will be administered at approximately 2, 6, and 10 hours post-dose.

5.5.3 Subject Activity Restrictions

Subjects should maintain their usual pattern of sun exposures and activities.

5.6 Treatment Compliance

Study treatment compliance will be assessed at all specified visits. The Investigator or assigned designee will perform drug accountability and dosing compliance calculations for all study drugs (number of capsules that should have been taken versus actual number taken as evidenced by written dosing records, subject dosing diaries, and the number of capsules remaining in bottles of study drug assigned to each subject). Dosing compliance at <80% or >120% should be reported as a protocol deviation.

5.7 Labeling

All study drug labels will include the protocol number, sponsor identification and address, study drug container contents, unique container number, area for subject and Investigator identification as applicable, investigational use statements, storage conditions, expiry date and instructions for use.

5.8 Storage and Accountability

All medications will be shipped to sites using standardized shipment and temperature monitoring procedures. While at the study site, all study drug will be stored in an area with light and heat protection and in accordance to USP Controlled Room Temperature (20-25°C or 68-77°F) and with access granted to authorized personnel only.

All sites must ensure that study drug has been kept under required conditions prior to dispensing. A temperature log recording the daily storage temperatures will be maintained at each site. Accountability for all study drugs, from receipt until final reconciliation and return of drug by the monitor or designee, will be the responsibility of the Investigator or the assigned designee(s).

In the case of temperature excursions, products should not be dispensed and the Investigator or the assigned designee(s) should contact the clinical monitor or the sponsor representative as soon as possible to receive further instructions.

The Investigator or assigned designee(s) will maintain study drug accountability records throughout the course of the study. Specifically, the Investigator or assigned designee will confirm that supplies are received intact and in the correct amounts per the shipping forms, and verify that the supplies were maintained within an appropriate temperature range during shipment. This will be documented by signing and dating the shipping forms and providing a copy to the sponsor or designee. A study drug accountability and dispensing log will record the study drug disposition, including dates, quantity of drug received by site, to whom and amount dispensed\returned and accounts of any drug accidentally destroyed, or not returned, or lost. The site's overall inventory of study drug supplies will be verified routinely throughout the course of the study. All opened and unopened bottles of study drug capsules are to be retained at the site until the sponsor or designee has performed a complete accountability, following which study drug will be returned to the sponsor or designee.

5.9 Investigational Product Retention at Study Site

At the conclusion of the study, a final accountability will be performed by the Investigator (or designee) and verified by the study monitor. Any discrepancies identified will be indicated, with a specific explanation of each discrepancy. The Investigator (or designee) must return all unused medication in accordance with the sponsor's instructions, and a copy of the clinical supplies return documentation will be returned to the sponsor or designee. Drug accountability records, clinical drug supply receipts, and return records must be maintained by the Investigator.

6 STUDY PROCEDURES

6.1 Informed Consent

A signed ICF will be obtained prior to any study related procedures. The subject or their legally authorized representative (LAR) will be permitted time and opportunity to inquire about details of the study and to decide whether or not to participate. The subject or their LAR will receive a copy of the signed and dated consent form and any written information provided to the study subjects. If any material change occurs that affects the conduct of the study or the subject's willingness to participate in the study, the subject or LAR will be required to sign an updated ICF.

The Investigator or his/her designee will explain the nature of all aspects of the study to the subject and/or their LAR, and answer all questions regarding this study, prior to obtaining informed consent.

The process for obtaining consent will be in accordance with all applicable regulatory requirements. The subject or his/her LAR and the Investigator or his/her designee must both sign and date the ICF before the subject can participate in the study. The original ICF will be retained in the site study records. The Investigator or his/her designee will ensure documentation of the consent discussion in the subject's medical record/source document. The decision by the subject to participate in the study is entirely voluntary. The Investigator or designee must emphasize to the subject that consent regarding study participation may be withdrawn at any time without penalty or loss of benefits to which the subject is otherwise entitled.

If the ICF or patient information is amended during the study, the Investigator must follow all applicable regulatory requirements pertaining to approval of the amended ICF by the Institutional Review Board/Ethics Committee (IRB/EC) and use of the amended form (including for ongoing subjects).

6.2 Medical History and Concomitant Medications

A detailed medical history, including demographics, will be recorded at Visit 1/screening. Concomitant medications will be reviewed with each subject and recorded at specified visit intervals throughout the study.

6.3 Physical Examination and Vital Signs

VS and PE will be performed by a licensed physician or by another suitably-qualified person where permitted by local regulations. Evaluations are presented in [Table 1](#).

Table 1 Evaluations

Physical Examination:	
• A brief PE including weight and height and excluding a urogenital examination will be performed during Visit 1 and Visit 16 or ET.
Vital Sign measurements:	
• Blood pressure, heart rate and respiratory rate, and body temperature in degrees Celsius will be measured prior to any scheduled blood draws or at ET after the subject has been sitting for at least 2 minutes.
Body height	
• Body height will be recorded to the nearest 1.0 cm at Visit 1 and Visit 16 or ET.
Body weight:	
• Body weight will be recorded to the nearest 0.1 kg at Visit 1 and Visit 16 or ET.
BM1	
• BMI will be calculated using the body weight divided by the body height squared and recorded to the nearest tenth of a decimal point at Visit 1 and Visit 16 or ET.

6.4 Clinical Laboratory Tests

6.4.1 *Laboratory Parameters*

Blood will be drawn and analyzed as specified in [Table 2](#). Urine samples will be collected and analyzed as specified in Table 2.

All serum calcium values will be adjusted based on serum albumin level of <4.0 g/dL.

All clinically significant abnormal laboratory values will be recorded as AEs and the Investigator will follow-up according to [Section 6.6.6 Clinical Significance](#).

Please refer to [APPENDIX 1 Schedule of Events](#) for specific time points.

Subjects will be in a seated or supine position during blood collection. Clinical laboratory tests are listed in Table 2.

Table 2 List of Laboratory Tests

Hematology:	Serum Chemistry:
Hematocrit	Albumin
Hemoglobin	Alkaline phosphatase
Mean corpuscular hemoglobin	Alanine aminotransferase
Mean corpuscular hemoglobin concentration	Aspartate aminotransferase
Mean corpuscular volume	Blood urea nitrogen
Platelet count	Calcium (corrected)
Red blood cell count	Carbon dioxide
White blood cell count	Chloride
Drugs of Abuse Screen (Urine)	Creatinine
Serum pregnancy test (only for females of child bearing potential)	Globulin
PK and CCI parameters:	Glucose
CCI	Glutamic oxaloacetic transaminase
	Glutamic pyruvic transaminase
	Lactate dehydrogenase
	Phosphorus
Serum calcifediol	Potassium
CCI	Sodium
	Total bilirubin
	Direct bilirubin
	Total cholesterol
	Total protein
	Triglycerides
	Uric acid
	Serum Partial Chemistry:
	Calcium (corrected)
	Phosphorus
	Albumin
	Serum hepatitis B & C screen
	Serum HIV screen
CCI	eGFR
	Urinary albumin excretion

